Appendix E. Patient Health Questionnaire PHQ-9 For Depression

PATIENT HEALTH QUESTIO	NNAIRE	- 9			72883
THIS SECTION FOR USE B	SY STUDY PE	ERSONNE	L ONLY.		
Were data collected? No ☐ (provide reason in comment	's)				
If Yes , data collected on visit date \square or specify da	te:	Mon-YYYY			
Comments:	55-1	mon-1111			
Only the nations (authors) should an	tou informa	tion onto	this augs	tionnoiro	
Only the patient (subject) should en	ter iniorina	lion onto	triis ques		•
Over the last 2 weeks , how often have you been by any of the following problems?	bothered	Not at	Several days	More than half the days	Nearly every day
Little interest or pleasure in doing things		0	1	2	3
2. Feeling down, depressed, or hopeless		0	1	2	3
3. Trouble falling or staying asleep, or sleeping too	much	0	1	2	3
4. Feeling tired or having little energy		0	1	2	3
5. Poor appetite or overeating		0	1	2	3
Feeling bad about yourself — or that you are a fa have let yourself or your family down	0	1	2	3	
7. Trouble concentrating on things, such as reading newspaper or watching television	0	1	2	3	
Moving or speaking so slowly that other people c noticed? Or the opposite — being so fidgety or r you have been moving around a lot more than us	0	1	2	3	
Thoughts that you would be better off dead or of yourself in some way	hurting	0	1	2	3
		Scoring Fo	OR USE BY S	TUDY P ERSOI	INEL ONLY
		+	+	+	·
			=	Total Score	»:
If you checked off any problems, how difficult have these problems made it for you to do your work, take care of things at home, or get along with other people?					
Not difficult Somewhat at all difficult □		Very fficult □		Extreme difficu	• 1
Developed by Drs. Robert L. Spitzer, Janet B.W. Williams, Kurt Copyright © 2005 Pfizer, Inc. All rights reserved. Reproduced w		lleagues, with	an education	nal grant from EP10905.PHQ9P	Pfizer Inc.
I confirm this information is accurate. Patient's/	Subject's initi	ials:	Date:		

Appendix F. Health Care Resource Utilization (Unscheduled Outpatient Visits, Emergency Room Visits and Hospitalizations)

1. Since the last study visit has the subject had any physician/health care visits for their Chronic Plaque Psoriasis other than the protocol visits?
☐ No ☐ Yes (if yes provide the following)
If yes provide the following:
I. Since the last visit, has the subject been seen by a physician for his/her Psoriasis?
YES: NO: If YES, how many times:
II. Since the last visit, has the subject been seen in the Emergency Room for his/her Psoriasis?
YES: NO: If YES, how many times:
III. Since the last visit, has the subject been admitted to the hospital due to his/her Psoriasis?
YES: NO: If YES, how many times: IF YES, please indicate the total number of days in the hospital:

Work Productivity and Activity Impairment Questionnaire: Specific Health Problem V2.0 (WPAI:SHP) Appendix G.

TDI C	11 '	,•				.1	CC .	c	_	NG OT	 .	u c	1.99.
								•					your ability to work
and pe	_												mber, as indicated.
1.	Are you cu If NO,									? _		NO _	YES
The no	ext question	ns are	abo	ut th	e pa	ast so	even	days	, not	incl	ludin	g toda	y.
2.	problems a	associ s you	ated wen	l witl t in l	n yo ate,	ur Pa left	SOR] early	[ASI] , etc.	S ? I , bec	nclu ause	de ho	ours yo	m work because of ou missed on sick SORIASIS. Do not
	НО	URS											
3.	_	-			•					•			m work because of ipate in this study?
	HO	URS											
4.	During the	e past	seve	en da	ys,	how	man	y hou	ırs di	id yo	ou ac	tually	work?
	HO	URS (If "()," sl	kip t	o qu	estio	n 6.)					
5.	During the productivi								you	r PS	ORL	ASIS a	affect your
	Think about days you were limited in the amount or kind of work you could do, days you accomplished less than you would like, or days you could not do your work as carefully as usual. If PSORIASIS affected your work only a little, choose a low number. Choose a high number if PSORIASIS affected your work a great deal.												
			Co				w mu						
				pro	duct	ivity	while	you	were	wor	king .		
	IASIS had ect on my	0	1	2	3	4	5	6	7	8	9	10	PSORIASIS completely prevented
WOIK						CIRC	TE 4	NII	MRF	(R			me from working
	CIRCLE A NUMBER												

6. During the past seven days, how much did your PSORIASIS affect your ability to do your regular daily activities, other than work at a job?

[figure not shown]
By regular activities, we mean the usual activities you do, such as work around the house, shopping, childcare, exercising, studying, etc. Think about times you were limited in the amount or kind of activities you could do and times you accomplished less than you would like. If PSORIASIS affected your activities only a little, choose a low number. Choose a high number if PSORIASIS affected your activities a great deal.

Consider only how much PSORIASIS affected your ability to do your regular daily activities, other than work at a job.

PSORIASIS had **PSORIASIS** no effect on my completely 0 1 2 3 5 6 7 8 9 10 4 daily activities prevented me from doing my daily activities

CIRCLE A NUMBER

WPAI:SHP V2.0 (US English)

[figure not shown]

Appendix H. Rosenberg Self-Esteem Scale

Instructions: Below is a list of statements dealing with your general feelings about yourself. If you strongly agree, circle **SA**. If you agree with the statement, circle **A**. If you disagree, circle **D**. If you strongly disagree, circle **SD**.

[figure not shown]
1.	On the whole, I am satisfied with myself.	SA	A	D	SD
2.	At times, I think I am no good at all.	SA	A	D	SD
3.	I feel that I have a number of good qualities.	SA	A	D	SD
4.	I am able to do things as well as most other people.	SA	A	D	SD
5.	I feel I do not have much to be proud of.	SA	A	D	SD
6.	I certainly feel useless at times.	SA	A	D	SD
7.	I feel that I'm a person of worth, at least on an equal plane with others.	SA	A	D	SD
8.	I wish I could have more respect for myself.	SA	A	D	SD
9.	All in all, I am inclined to feel that I am a failure.	SA	A	D	SD
10.	I take a positive attitude toward myself.	SA	A	D	SD

Rosenberg M. Society and the adolescent self-image. Princeton, NJ: Princeton University Press; 1965.

[figure not shown]

Appendix I. Census Socio-Demographic Questionnaire

1.	Are you from	a Spanish/Hispanic/Latino background?
	☐ Yes	
	☐ No,	not Spanish/Hispanic/Latino
2.	What is the hi	ghest level of education you have completed? (check one answer)
	Les	s than high school
	☐ Hig	h school
	Ass	ociate degree, technical, or trade school
	☐ Col	lege
	☐ Gra	duate school
	Oth	er
3.	What is your r	narital status?
	☐ Nov	w married (if checked, proceed to question 4)
	☐ Wio	lowed
	Div	orced (if checked, proceed to question 5)
	☐ Sep	arated
	☐ Nev	ver married
	If you checked	"now married" or "divorced" above, please answer questions 4 and 5.
4.	If you are curr	ently married, is this your:
	Firs	t marriage
	☐ Sec	ond marriage
	Thi	rd marriage
	Gre	ater than third marriage
5.	If you are dive	orced, is this your:
	Firs	t divorce
	☐ Sec	ond divorce
	☐ Gre	ater than second divorce

[figure not shown]

6.	What is y	our current work status?
		Working for pay at a job or business
		Unemployed
		Working, but not for pay, at a family-owned job or business
		rently have a job or business, proceed to question 7. rently do not have a job or business, proceed to question 8.
7.	What cate	egory below best describes your current job or business?
		Administrator, Manager
		Teacher
		Professional
		Administrative support, including clerical
		Sales, retail
		Sales, business goods and services
		Technician
		Protective service
		Private household service
		Other service
		Machine operator, assembler, inspector
		Transportation operator
		Handler, helper, laborer
		Mechanic, repairer, precision production
		Construction, mining
		Farming
		Forestry, fishing, groundskeeping
		Armed forces
8.	What is the	he main reason you do not have a job or business?
		Taking care of house or family
		Going to school
		Retired
		On family or maternity leave
		Disabled

9.	What was sources)?	your overall income last year (from wages or salary, tips, commissions, bonuses and other
		< \$5,000
		\$5,001 - \$10,000
		\$10,001 - \$20,000
		\$20,001 - \$30,000
		\$30,001 - \$40,000
		\$40,001 - \$50,000
		\$50,001 - \$75,000
		\$75,001 - \$100,000
		\$100,000 or more

Census's American Community Survey (ACS) (www.census.gov), Bureau of Labor Statistics surveys (www.bls.gov), and the Medical Expenditure Panel Survey (MEPS) (www.meps.ahrq.gov)

[figure not shown]

Appendix J. Medical Outcomes (MOS)-Social Activities Scale

The next questions ask about your social activities.

suons	ask about your social activi	nes.
1.		s, how much of the time has your physical health or emotional th your social activities (like visiting with friends, relatives, etc.)?
		(Circle One)
		All of the time1
		Most of the time2
		A good bit of the time3
		Some of the time4
		A little of the time5
		None of the time6
2.		al level of social activity, has your social activity during the past 6 sed the same, or increased because of a change in your physical or
		(Circle One)
		Much less socially active than before
		Somewhat less socially active than before
		About as socially active as before3
		Somewhat more socially active than before
		Much more socially active than before5
3.	Compared to others yo physical health or emo	our age, are your social activities more or less limited because of your tional problems?
		(Circle One)
		Much more limited than others1
		Somewhat more limited than others2
		About the same as others3
		Somewhat less limited than others4
		Much less limited than others

[figure not shown]

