10.4 Effectiveness Analyses

Effectiveness parameters measured in this registry for patients enrolled in the US include: Physician's Global Assessment (PGA), Dermatology Life Quality Index (DLQI), Patient Health Questionnaire PHQ-9 For Depression (PHQ-9), Healthcare Resource Utilization, Work Productivity and Activity Impairment (WPAI:SHP), Rosenberg Self-Esteem Scale, Census Socio-Demographic Questionnaire, Medical Outcomes (MOS)-Social Activities Scale, Psoriasis Impact and Experience, Illness Cognition Questionnaire, Insurance Status, and Patient Global Assessment.

[figure not shown]
Descriptive statistics will be provided for the following variables according to the collection schedule outlined in Table 1:

- 1. PGA:
 - a. Proportion of patients achieving "clear."
 - b. Proportion of patients achieving "clear or minimal."
- 2. DLQI:
 - a. Proportion of patients achieving DLQI = 0.
 - b. Proportion of patients achieving DLQI = 0 or 1.
 - c. Change from baseline in DLQI.
- 3. PHQ9:
 - a. Change from baseline in PHQ9 total score.
- 4. Health Resource Utilization

- a. Proportion of subjects who had at least one event (e.g., hospitalization, ER, physician visits).
- b. Average number of events occurred per subjective who had at least one event.
- 5. WPAI-SHP: Change from baseline in the four impairment percentages:
 - a. Percent work time missed.
 - b. Percent impairment while working.
 - c. Percent impaired activity.
 - d. Percent overall work impairment.
- 6. Rosenberg Self-Esteem Scale: change from baseline in total score.
- 7. Census Socio-Demographic Variables: proportion of subjects in each category.
- 8. Medical Outcomes (MOS)-Social Activities Scale: change from baseline.
- 9. Psoriasis Impact and Experience: proportion of subjects who strongly agree, agree, not sure but probably agree, not sure but probably disagree or strongly disagree with any of the statements.
- 10. Illness Cognition Questionnaire: change from baseline in helplessness sub-score, acceptance sub-score and total score.
- 11. Insurance Status: proportion of subjects uninsured, or insured in any of the plan types.
- 12. Patient Global Assessment:
 - a. Proportion of patients achieving "Complete disease control."
 - b. Proportion of patients achieving "Complete disease control or good disease control."

Effectiveness data will be analyzed as observed, as this is an observational registry. Number of patients with non-missing baseline and visit values, baseline mean, visit mean,

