Activity	Registry Enrollment	Month ^a	Month ^a	Month ^a	Month ^a 18, 24, 30, 36, 42, 48, 54	Month ^a	Month ^a 66, 72, 78, 84, 90, 96, 102, 108, 114	Upon Completion Month ^a 120 or Premature Discontinuation	At Time of Reported Event
Inclusion/Exclusion Criteria	X								
Informed Consent	X								
Demographics	X								
Medical History and Treatment Modality	X								
Safety Data Collection (AEs of Special Interest/SAEs)	X	X	X	X	X	X	X	X	X
Prior and Concomitant Psoriasis Medications	X	X	X	X	X	X	X	X	X
Concomitant Medications at Time of Reported SAE or AE of Interest	X	X	X	X	X	X	X	X	X
Physician Global Assessment	X	X	X	X	X	X	X	X	
PROs ^b									
Patient Global Assessment	X	X	X	X	X	X	X	X	
DLQI	X		X	X	X ^c	X	X ^c	X	
PHQ-9	X		X	X	X ^c	X	X ^c	X	
Healthcare Resource Utilization (Unscheduled Outpatient Visits, Emergency Room Visits and Hospitalizations Questionnaire)	X		X	X	X ^c	X	X ^c	X	
WPAI	X		X	X	X ^c	X	X ^c	X	

[figure not shown]

Table 1. **Registry Activities (Continued)**

Activity	Registry Enrollment	Month ^a	Month ^a	Month ^a	Month ^a 18, 24, 30, 36, 42, 48, 54	Month ^a	Month ^a 66, 72, 78, 84, 90, 96, 102, 108, 114	Upon Completion Month ^a 120 or Premature Discontinuation	At Time of Reported Event
Rosenberg Self-Esteem Scale	X			X		X		X	
Census Socio-Demographic Questionnaire	X					X		X	
Medical Outcomes (MOS)-Social Activities Scale	X			X		X		X	
Psoriasis Impact and Experience	X			X		X		X	
Illness Cognition Questionnaire	X			X		X		X	
Insurance Status	X			X		X		X	
Case Report Form Completion	X	X	X	X	X	X	X	X	X

Obvie HUMIRA® (adalimumab) P10-023 Protocol Amendment 3 Psoriasis HUMIRA® Registry

Section 6.5.3 Medical History Third paragraph previously read:

Patients rolling over from a prior psoriasis clinical trial will be asked to provide medical history only for previously unreported conditions and/or conditions not requested to be reported in the original study of participation.

Has been changed to read:

[figure not shown]
Patients rolling over from a prior HUMIRA® clinical trial will be asked to provide medical history only for previously unreported conditions and/or conditions not requested to be reported in the original study of participation.

Section 6.5.4 Prior and Concomitant Medications Add: new third paragraph

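### Section 10.4 takes change from baseline on the whole MOS Social Activities Scale, although item 2 is itself a change rating and its difference cannot be read as change in social activity

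*Protocol*

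**What the plan says.** Section 10.4, item 8, fixes the analysis as "Medical Outcomes (MOS)-Social Activities Scale: change from baseline". The closing text of 10.4 adds that continuous variables are summarised by baseline mean, visit mean, and mean and standard deviation of change, as observed.

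Appendix J prints three items:

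- **Item 1** asks how much of the time health interferes with social activities. It has six options, ending in "None of the time6" (the final digit is the printed code). It measures a level.
- **Item 2** compares recent social activity with the patient's usual level; its stem contains the words "level of social activity, has your social activity during the", followed by the recall period. The five options run from "Much less socially active than before" through "About as socially active as before3" to "Much more socially active than before5". It measures a change.
- **Item 3** asks how limited the patient is compared with others of the same age, on five options. It measures a level relative to peers.

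Table 1 schedules the scale at enrollment, at two intermediate visits (Months 12 and 60 by column order) and at Month 120 or premature discontinuation, at US sites only. For some instruments 10.4 names the score to be used: a total for the PHQ-9 and the Rosenberg scale, and sub-scores plus a total for the Illness Cognition Questionnaire. It names none for the MOS scale.

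**The concern.** Subtracting an enrollment value makes sense for an item that records where the patient stands. Item 2 records how the recent past compares with what came before or with what is usual. Its enrollment answer describes the period before enrollment and its later answer describes the period before that visit, so the difference is not the change in social activity between the two dates. A later answer of 3 is compatible with a stable low level, a stable recovered level, or no effect at any time.

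Two features of the registry make this more than a formality. Patients who have just started HUMIRA (Section 6.1.1) may enrol after a recent decline and give low answers. Patients already on continuous HUMIRA may enrol after a recent improvement and give high answers. Both groups belong to the All Treated Patient Population (Section 10.1), over which effectiveness is summarised. At stake is whether the reported mean change on this scale can be interpreted.

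**Working it through.** No figure in the protocol depends on this point, so there is none to reproduce. The check is score arithmetic.

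**Inputs.** From Appendix J: item 1 coded 1 to 6, items 2 and 3 coded 1 to 5, higher being better. Code 1 for the lowest answer on item 2 is inferred from option order. Assumed, because the protocol gives no scoring rule: a raw sum of the three items or, alternatively, the mean of the items each rescaled to 0-100.

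**Weight of item 2.** The raw sum runs from 1+1+1 = 3 to 6+5+5 = 16, a range of 13. Item 2 contributes 5-1 = 4, and 4/13 = 31%. In the rescaled mean it carries one third.

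**One patient.** A shift of 2 on item 2 alone moves the rescaled mean by (2/4) x 100/3 = 16.7. A shift of 1 moves it by (1/4) x 100/3 = 8.3.

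**Patterns.** Each triple gives items 1, 2 and 3 at enrollment and then at the later visit. The values are illustrative.

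| Pattern | Enrollment | Later | Item 2 | Sum | 0-100 |
|---|---|---|---|---|---|
| A. Fell within the recall window before enrollment, never recovered, later judges against the recent past | 3,1,2 | 3,3,2 | +2 | +2 | +16.7 |
| B. As A, but still judges against the level before the fall | 3,1,2 | 3,1,2 | 0 | 0 | 0 |
| C. Fell earlier than the window before enrollment, judges against the recent past | 3,3,2 | 3,3,2 | 0 | 0 | 0 |
| D. Fell after enrollment, outside the window at the visit | 5,3,3 | 3,3,2 | 0 | -3 | -21.7 |
| E. Fell within the window before the visit | 5,3,3 | 3,1,2 | -2 | -5 | -38.3 |
| F. Gained after enrollment, sustained and older than the window | 3,3,2 | 5,3,3 | 0 | +3 | +21.7 |
| G. Improved shortly before enrollment and stayed well | 5,5,3 | 5,3,3 | -2 | -2 | -16.7 |

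A is a false gain and G a false decline. In D and F item 2 misses a real change that items 1 and 3 show.

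**Group level, illustration only.** Let p1, p2, p4 and p5 be the shares answering 1, 2, 4 and 5 at enrollment, and suppose everyone later answers 3 with no real change. The mean shift on item 2 is 2(p1 - p5) + (p2 - p4).

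- With p1 = 20%, p2 = 30% and none at 4 or 5: 2(0.20) + 0.30 = 0.7 raw, or 0.7/4 x 100/3 = 5.8 on 0-100.
- With 10% and 20%: 0.4 raw, or 3.3. With 30% and 40%: 1.0 raw, or 8.3.
- With the first case mirrored (p5 = 20%, p4 = 30%, none at 1 or 2): -0.7 raw, or -5.8. With both sides present in equal shares: 0.

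The protocol gives no answer distribution, so neither the size nor the sign can be fixed.

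**The case against.** The strongest case on the other side has four parts.

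- **The anchor.** The stem of item 2 refers to the usual level. A patient who keeps the level before the fall in mind answers the same way again, and the change is zero (pattern B). This stands as a limit on the artefact. It does not remove it, because the answer options compare with before, and nothing fixes the reference over ten years.
- **Scoring.** The protocol defines no composite, and a scoring rule may properly sit in an analysis plan that is not shown. The cited source of the scale cannot be consulted either. This stands for the 31% and 16.7 figures, which need a composite. It does not answer the core point: 10.4 already commits the scale to change from baseline, and any score that contains item 2 inherits the problem. If items are reported singly, items 1 and 3 are unaffected.
- **Recall window.** The unit after the 6 in item 2 is not legible in the text available, so how far back the item reaches is uncertain. Even if it is months, a patient who discontinues within six months of enrollment completes the scale with a window that reaches back to enrollment. So it cannot be said that the window never does.
- **Importance.** This is one of twelve listed effectiveness measures, descriptive, as observed and US-only. That stands and sets the severity.

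A reader might infer that patients whose social life fell and never recovered will generally score as improved, so that the scale is biased in favour of HUMIRA. The documents do not support this. A false gain needs a fall inside the window before enrollment, a patient who has since reset what is usual, and no offsetting fall on items 1 and 3. Of the seven patterns above only A produces it, and G produces the opposite.

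**Conclusion.** The point holds in limited form. For item 2, change from baseline is a difference between two change ratings and cannot be read as change in social activity. It can mislead in either direction for a single patient, and it can miss sustained gains. The net direction in the All Treated Patient Population is unknown.

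The possible weight is 4 of 13 raw points (31%) if the items are summed, or one third if they are rescaled and averaged. Both depend on an assumed scoring rule. The group-level shifts of 3.3 to 8.3 points rest on assumed answers and illustrate the mechanism without estimating bias.

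Severity is minor. No test, sample size or safety analysis depends on this scale, and it is one descriptive measure under the secondary objective.

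**What to change.** Reword Section 10.4, item 8, along these lines: report change from baseline for items 1 and 3. Report item 2 at each scheduled visit as the percentages of patients less, equally and more socially active than usual, without subtracting the enrollment answer. Keep the published full-scale score alongside for comparability, state how it is scored, and note that it contains a transition item.

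Section 10.4 already reports the Psoriasis Impact and Experience items by response category, so the format for item 2 is not new to the plan. The change costs one line and needs no new data. The downside is that the full-scale change is no longer the only MOS result, so there is slightly more to present and explain.

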Appendix K. Psoriasis Impact and Experience

Instructions: The following lists several statements by people with psoriasis. Please indicate the extent to which you agree or disagree with each of the statements.

	n you agree of disagree with each of		Ones.	Not Sure but	Not Sure but		G. 1
		Strongly Agree	Agree	Probably Agree	Probably Disagree	Disagree	Strongly Disagree
1	I sometimes avoid social situations because of psoriasis.						
2	If I thought an employer might discriminate against someone because of psoriasis, I would not apply for the job.						
3	An employer who knows a person has a history of psoriasis will probably pass over the application and give the job to someone else.						
4	People do not want to be my friend when they learn I have psoriasis.						
5	I would not apply or get training for a job that involved dealing with the public because of my psoriasis.						
6	I feel the need to hide the fact that I have psoriasis.						
7	I feel embarrassed because of my psoriasis.						
8	I sometimes think that I am rejected or treated with caution because of my psoriasis.						
9	I have the feeling that I am worth less than others.						
10	When skin has broken out badly, there are times when I think that life is not worth living.						
11	I try to dress in a way that makes my psoriasis as unnoticeable as possible.						

Items 1–5 from the Feelings of Stigmatization Questionnaire (Ginsburg & Link 1989)

[figure not shown]
Items 6–11 from the Questionnaire for the Experience of Skin Complaints (QES) (Schmid-Ott et al. 1996)

